6.1.2. Definitions

6.1.2.1. Study Time Intervals

Induction Period

All subjects who were randomized to the study are considered as entering the Induction Period.

The start of the Induction Period is defined as the date of first injection following randomization. For subjects who were randomized but not dosed, the Induction Period starts at the randomization date.

The end of the Induction Period is defined as the date of PASI measurement at Week 16, or the early termination date if subjects discontinued from study prior to or at Week 16, or Day 117, whichever comes first.

Maintenance Period

All subjects who had Week 16 visit with PASI measurement (except the ones discontinued the study at Week 16) are considered to have entered the Maintenance Period.

The start of the Maintenance Period is defined as the same date as end of the Induction Period, which is the date of PASI measurement at Week 16.

The end of the Maintenance Period is defined as the visit date at Week 104, or the date when the subjects received rescue treatment, or the early termination date if subjects discontinued from study prior to or at Week 104, whichever comes first.

Rescue Period

All subjects in PRN groups who received at least 1 dose of rescue treatment are considered to have entered the Rescue Period, and will be included in the Rescue Period analysis population.

The start of the Rescue Period is defined as the date the patient received the first dose of rescue treatment.

The end of the Rescue Period is defined as the visit date at Week 104, or early termination date if subjects discontinued from study prior to or at Week 104, whichever comes first.

Follow-up Period

All subjects who had Visit 29 are considered to have entered the Follow-up Period, and will be included in the Follow-up Period analysis population.

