## 2. Schedule of Activities

Induction Dosing Period (Visits 1-7)								
Visit No.	V1	V2	V3	V4	V5	V6	V7	Comments
Week Relative to Study Drug Start	-4	0	2	4	8	12	16	All activities should be completed prior to any study dose administration unless otherwise stated below.
Day with Visit Tolerance Interval	≤28 from V2	0	14 ± 2	28 ± 3	56 ± 5	84 ± 5	112 ± 5	Visit 1 procedures may be conducted over more than 1 day as long as all tasks are completed within the allowable visit tolerance (at least 3 days should be allowed for receipt of laboratory test results).
Informed consent	X							
Demographics	X							
Height	X							
Physical examination & weight	X	X					X	One complete physical examination (excluding pelvic, rectal, and breast examinations) will be performed at screening. All physical examinations throughout the study should include a symptom-directed evaluation as well as examination of heart, lungs, and abdomen and visual examination of all skin areas (including genitalia and breast areas).
Review & confirm inclusion/exclusion criteria	X	X						
Complete medical/surgical history and habits	X							
Concomitant medications	X	X	X	X	X	X	X	
Preexisting conditions	X							
Adverse events	X	X	X	X	X	X	X	

Induction Dosing Period (Visits 1-7)								
Visit No.	V1	V2	V3	V4	V5	V6	V7	Comments
Week Relative to Study Drug Start	-4	0	2	4	8	12	16	All activities should be completed prior to any study dose administration unless otherwise stated below.
Day with Visit Tolerance Interval	≤28 from V2	0	14 ± 2	28 ± 3	56 ± 5	84 ± 5	112 ± 5	Visit 1 procedures may be conducted over more than 1 day as long as all tasks are completed within the allowable visit tolerance (at least 3 days should be allowed for receipt of laboratory test results).
Vital signs (BP and heart rate), body temperature only at V1 and V2, unless clinically indicated	X	X	X	X	X	X	X	Sitting blood pressure and pulse, to be obtained at approximately the same time as ECG measurements or blood sampling. When multiple assessments are scheduled for the same time point, the order of completion should be as follows: ECG, vital signs, and then blood sampling.
Chest radiography for TB screening (required only if not already done within 3 months prior to screening)	X							Chest radiography (Section 9.4.4.1) will be performed at screening unless such radiography has been performed within 3 months before initial screening (provided the radiographs and/or formal report are available for the investigator’s review).

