6.1.1. Subject Populations for Analyses

For purposes of analysis, populations for analyses are described in [Table 6.1](#).

Table 6.1. Subject Populations for Analyses

Population	Description
Intent-to-treat (ITT) (Induction Period Efficacy)	All randomized subjects, even if the subject does not take the assigned treatment, does not receive the correct treatment, or otherwise does not follow the protocol: 
 Unless otherwise noted, efficacy and health outcomes analyses for the Induction Period will be conducted on this population. Subjects will be analyzed according to the treatment to which they were assigned.
Induction Period Safety	All randomized subjects who received at least 1 dose of study treatment: 
 Unless otherwise noted, safety analyses for the Induction Period will be conducted on this population. Subjects will be analyzed according to the treatment to which they were assigned.
Maintenance Period Efficacy	All randomized subjects who have entered the Maintenance Period (see definition of entering Maintenance Period in Section 6.1.2.1): 
 Unless otherwise noted, efficacy, and health outcomes for the Maintenance Period will be conducted on this population. Subjects will be analyzed according to the treatment to which they were assigned in Maintenance Period.

Population	Description
Maintenance Period Safety	
All randomized subjects received at least 1 dose of study treatment who have entered the Maintenance Period (see definition of entering Maintenance Period in Section 6.1.2.1):
 
 • Unless otherwise noted, safety analyses for the Maintenance Period will be conducted on this population. • Subjects will be analyzed according to the treatment to which they were assigned in Maintenance Period, with all LY3074828 300 mg Q8W arms combined, that is, there will be 4 treatment groups in the Maintenance Period: 
 ○ LY 300 mg PRN ○ LY 100 mg PRN ○ LY 30 mg PRN ○ LY 300 mg Q8W (including subjects from 4 Induction Period treatment groups)

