6.12. Safety Analyses

All safety evaluations will be based upon the Safety Population as defined in Section [6.1.1](#).

Safety and tolerability will be evaluated in terms of adverse events (AEs), treatment-emergent AEs (TEAEs), discontinuations due to AEs, deaths, other SAEs, permanent discontinuations and interruptions of study drug, laboratory analyses including neutrophil counts and immunogenicity, Columbia Suicide Severity Rating Scale (C-SSRS), vital signs, echocardiogram (ECG) findings, and concomitant medications.

The Induction Period safety analyses will summarize each LY3074828 dose regimen (300 mg, 100 mg, and 30 mg) and compare the pooled LY3074828 dose regimens to placebo. Treatment group comparisons will be analyzed using the methods described in Section [6.1.3](#).

For the Maintenance Period, safety will be summarized by treatment (each PRN arm and 300 mg Q8W). No comparisons will be conducted. Only events occurred in the Maintenance Period will be included in this analysis, that is, no events in the Rescue Period will be included. Only a

smaller set of safety analyses (for example, TEAE, serious adverse events (SAE), AE leading to study treatment discontinuation, TE high/low labs, TE high/low vitals) will be needed for the Maintenance Period.

In addition, an overall summary of safety for all LY3074828 exposed subjects, will be provided by presenting all LY3074528 arms pooled including the Induction, Maintenance, and Rescue Periods; Follow-Up Period separately (if there are meaningful number of subjects); and All Periods + Follow-up Period. Only a smaller set of safety analyses (for example, TEAE, SAE, AE leading to study treatment discontinuation, TE high/low labs, TE high/low vitals) will be needed for the overall safety summary.

Safety event occurring on the same day of the end of a period and the start of next period will be counted towards the next period, for example, if a safety event occurred on the date of PASI measurement at Week 16, the event will be allocated to the Maintenance Period.

Change from baseline analyses will use baseline definition provided in Section 6.1.2.

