6.12.1. Extent of Exposure

6.12.1.1. Duration of Exposure

Duration of exposure to study treatment (defined as time since first injection of study treatment in days) will be summarized by treatment group during the Induction Period, the Maintenance Period, and the combined Induction Period, Maintenance Period, and Rescue Period.

Duration of exposure during the Induction Period will be calculated as:

$$(Date\ of\ last\ study\ visit\ in\ the\ Induction\ Period - Date\ of\ first\ injection\ of\ study\ treatment + 1)$$

Duration of exposure during the Maintenance Period will be calculated as:

$$(Date\ of\ last\ study\ visit\ in\ Maintenance\ Period - Date\ of\ last\ study\ visit\ in\ the\ Induction\ Period + 1)$$

Duration of exposure during the Rescue Period will be calculated as:

$$(Date\ of\ last\ study\ visit\ in\ Rescue\ Period - Date\ of\ First\ Rescue\ Treatment + 1)$$

Duration of exposure to LY3074828 for the combined Induction Period, Maintenance Period, and Rescue Period will be calculated as:

$$(Date\ of\ last\ study\ visit\ in\ the\ Maintenance\ Period - Date\ of\ first\ injection\ of\ LY3074828 + 1)$$

for subjects without rescue and

$$(Date\ of\ last\ study\ visit\ in\ the\ Rescue\ Period - Date\ of\ first\ injection\ of\ LY3074828 + 1)$$

for subjects with rescue

For the combined Induction Period, Maintenance Period, and Rescue Period summaries, exposure will be summarized for all LY3074828 dosing regimens pooled.

Descriptive statistics will be provided for patient days of exposure and the frequency of patients falling into the following different exposure ranges (that is, only the exposure ranges that fall within the treatment period will be presented) will be summarized:

- >0, ≥7 days, ≥14 days, ≥30 days, ≥60 days, ≥90 days, ≥120 days, ≥183 days, ≥365 days, ≥548 days.
- >0 to <7 days, ≥7 to <14 days, ≥14 to <30 days, ≥30 to <60 days, ≥60 to <90 days, ≥90 to <120 days, ≥120 to <183 days, ≥183 to <365 days, ≥365 days to <548 days, and ≥548 days.

Additional exposure ranges may be considered if necessary.

A by-patient listing of exposure duration will be provided.

No inferential analysis for comparison between treatment arms will be performed.

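### SAP 6.1.2.1 gives two conflicting Induction/Maintenance boundaries when the Week 16 (Visit 7) PASI is taken after Day 117

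*SAP*

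**What the plan says.** SAP 6.1.2.1 ends Induction at the earliest of three dates: the Week 16 PASI, "or the early termination date if subjects discontinued from study prior to or at Week 16, or Day 117, whichever comes first". The cap is not limited to subjects who lack a Week 16 PASI.

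The same section defines who enters Maintenance: "All subjects who had Week 16 visit with PASI measurement (except the ones discontinued the study at Week 16"). This rule has no date limit. The start of Maintenance is "defined as the same date as end of the Induction Period, which is the date of PASI measurement at Week 16".

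Three other places depend on that boundary:

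- SAP 6.12 counts events on a shared boundary date in the later period. Its example is that "if a safety event occurred on the date of PASI measurement at Week 16, the event will be allocated to the Maintenance Period".
- SAP 6.12.1.1 ("Duration of exposure during the Maintenance Period will be calculated as") takes the last Maintenance visit minus the last Induction visit, plus 1.
- SAP Table 6.1 pools one Maintenance safety group as "LY 300 mg Q8W (including subjects from 4 Induction Period treatment groups").

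The protocol's Schedule of Activities sets Visit 7 at Day 112 ± 5 with Visit 2 as Day 0, and lists Visit 7 under the Induction period.

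**The concern.** Day 117 is a sensible stop for a subject with neither a Week 16 PASI nor a termination date. As worded, it also applies to a subject who attends Visit 7 late, is assessed, and goes on to Maintenance. Induction then closes before the assessment that decides the next treatment, and the sentence that starts Maintenance names two dates that no longer coincide.

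Late visits are foreseeable. Protocol 7.6 and SAP 6.7 define noncompliance by the visit window, and SAP 6.16 keeps every protocol violator in the ITT population.

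What is at stake is mainly safety bookkeeping. Induction is the only placebo-controlled safety comparison, so events shortly before a late Visit 7 should stay in it. They should not be unassigned, or be listed under a treatment the subject had not yet received. Two programmers could also derive different period dates and exposure from the same text.

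**Working it through.** **Inputs**

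- Visit 7 window: Day 112 ± 5; Visit 6 window: Day 84 ± 5; Visit 2 is Day 0 (protocol, Schedule of Activities).
- Order at a visit: "All activities should be completed prior to any study dose administration unless otherwise stated below". The Visit 7 PASI therefore precedes any Week 16 dose, and a placebo subject has had no LY3074828 before it.
- Maintenance length: 88 weeks. Placebo arm: 50 subjects.
- Assumed, because the documents give no figure: how late Visit 7 is, and for how many subjects.

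**Step 1. Origin of Day 117.** 112 + 5 = 117, the upper limit of the Visit 7 window with Visit 2 as Day 0. If the first injection is counted as Day 1, the last in-window day is 117 + 1 = 118, which is already past the cap. The SAP does not state its convention.

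**Step 2. The conflict.** Let the Visit 7 PASI fall on Day 117 + L, with L > 0. Induction ends on Day 117. Maintenance starts on Day 117 by the end-of-Induction wording, and on Day 117 + L by the PASI-date wording. The two agree only when the PASI is on or before Day 117.

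**Step 3. Where the L days go.**

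- *Maintenance starts at the PASI date:* the interval belongs to neither period. In whole calendar dates, Day 118 to Day 116 + L are unassigned, which is L − 1 dates.
- *Maintenance starts on Day 117:* Day 117 to Day 116 + L, which is L dates, fall in Maintenance before the new treatment. The boundary-date rule in SAP 6.12 moves Day 117 as well. For a placebo subject these dates sit in LY 300 mg Q8W.

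**Step 4. Exposure formula.** If visits are assigned by label, Visit 7 remains the last Induction visit. Induction exposure is 117 + L + 1 days and nothing moves. If visits are assigned by date, the last Induction visit is Visit 6. Induction exposure is then 84 − 0 + 1 = 85 days, and Maintenance gains (117 + L) − 84 = 33 + L days. The range below uses Visit 6 on Day 89 or Day 79.

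| L | Visit 7 day | Days from Day 117 to Visit 7 | Days added to Maintenance exposure, by date only |
|---|---|---|---|
| 1 | 118 | 1 | 34 (29 to 39) |
| 2 | 119 | 2 | 35 (30 to 40) |
| 7 | 124 | 7 | 40 (35 to 45) |
| 14 | 131 | 14 | 47 (42 to 52) |

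**Step 5. Scale, by assumption.** Suppose 5 of 50 placebo subjects are each 7 days late. Planned Maintenance time for 50 subjects is 50 × 88 × 7 = 30,800 days.

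- Interval in question: 5 × 7 = 35 days; 35 / 30,800 = 0.1%.
- Exposure formula by date: 5 × 40 = 200 days; 200 / 30,800 = 0.65%.

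The pooled LY 300 mg Q8W group also takes subjects from the LY arms, so its denominator is larger and the shares smaller.

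**Step 6. Efficacy rows.** The primary PASI 90 row of Table 6.3 names Week 16. The NRI rule in SAP 6.3.1 turns on data missing at the analysis time point. Neither cites the Induction end date. The Induction rows for PASI 75, PASI 100, sPGA, DLQI, PatGA, PSS and SF-36 instead cover all post-baseline Induction visits. If period membership is decided by date, a late Visit 7 drops out of those rows. SF-36 has only one post-baseline Induction visit, Visit 7, so it would have no Induction value for that subject.

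**The case against.** The strongest reply is that the SAP's other wording largely settles the matter. The Maintenance sentence itself names the PASI date, and the example in SAP 6.12 uses it. The protocol lists Visit 7 as an Induction visit, and SAP 6.1.3 names Week 16 as Visit 7 among the post-baseline Induction visits. On these anchors no exposure moves. Maintenance safety is descriptive, exposure-adjusted rates are produced only if needed, and pooled LY exposure starts at the first LY injection, so it excludes placebo time. Under Day 0 numbering only out-of-window visits are affected.

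Most of this stands, and it rules out two stronger readings that a reader might infer:

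- *Placebo time is credited to LY 300 mg Q8W.* This needs Maintenance to start on Day 117, or the exposure formula to be applied with visits assigned by date. The PASI-date wording points to a gap instead. The 35-day shift for a Day 119 visit holds only under assignment by date.
- *Late PASI 90 responders become nonresponders in the primary analysis.* No text applies Day 117 to the Week 16 time point, so a loss of responders cannot be derived from the plan. As a bound, exact Fisher power for 60% versus 3% with 50 per arm is 0.9999999. It stays above 99.99% even if 2% to 20% of Week 16 values in both arms were set to nonresponse.

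The reply does not remove the conflict. The PASI-date anchor leaves Induction closed at Day 117, so pre-Visit 7 events after that day still have no period.

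**Conclusion.** The contradiction is established from the text alone: for any Visit 7 PASI after Day 117, the end of Induction and the start of Maintenance cannot both be applied as written. The better-supported consequence is a gap of L days (L − 1 whole dates). Early entry into Maintenance is the alternative. Misplaced exposure, or missing values in the rows covering all Induction visits, follows only if visits are assigned by date. The primary endpoint is not shown to be affected.

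The scope is visits after Day 117: out of window if Visit 2 is Day 0, and also the last in-window day if the first injection is Day 1. With no late-visit count in the documents, the 0.1% and 0.65% figures are illustrations. The numerical effect is likely small. The point is still worth correcting, because it concerns events in the only placebo-controlled safety period and is cheap to settle.

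**What to change.** In SAP 6.1.2.1:

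1. End Induction at the Week 16 (Visit 7) PASI date whenever one exists, otherwise at the early termination date. Use Day 117 only when there is neither.
2. Start Maintenance at the Visit 7 PASI date for everyone who enters it, and count Maintenance exposure in SAP 6.12.1.1 from that date.
3. State that the Visit 7 assessment is the Week 16 value whatever day it was taken, for every Table 6.3 row that uses Induction visits.
4. State whether the first injection is Day 0 or Day 1.

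With the first two changes no day is unassigned or moved early, however late Visit 7 is. The cost is a few sentences in the SAP and one line of period-derivation code. No new data are needed.

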6.1.2.2. Definition of Study Baseline

For efficacy, health outcomes, and safety analyses, study baseline is defined as the last non-missing assessment (including unscheduled visits) before the first injection, which in most cases will be the measure recorded at Week 0 (Visit 2). For efficacy/health outcome measures, if the patient does not take any injection, the last available value on or prior to randomization date will be used.

For PSS, the weekly average of at least 4 days of the consecutive 7 days prior to the first injection will be the study baseline score.

In cases where baseline measurements are taken on the same day as injection and no times are recorded, it will be assumed that these measurements are taken prior to the injection.

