### 10.3.1.2. General Considerations for Analyses in the Maintenance Period

For maintenance period efficacy analysis, unless otherwise stated, baseline is defined as the last available value before the initial randomization in the induction period which in most cases will be the value recorded at Week 0 (Visit 2).

For maintenance period safety analysis, for subjects

- randomized to placebo in the induction period and for subjects who did not achieve PASI 90, baseline is defined as the last available value before the treatment reassignment in the maintenance period (Week 16, Visit 7)
- who did achieve PASI 90, baseline is defined as the last available value before the initial randomization which in most cases will be the measure recorded at Week 0 (Visit 2)

Change from baseline and 95% confidence interval will be calculated by treatment as the visit value of interest minus the baseline value for continuous variables. The proportion and 95% confidence interval will be reported by treatment for categorical variables.

The Kaplan-Meier product limit method will be used to estimate the survival curves for time-to-event variables; median time to loss of response will be summarized by treatment.

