In the 3-panel display to assess low values, the scatterplot will plot the minimum value during the baseline period versus the minimum value during the treatment period. Lines indicating the reference limits are included. In cases where limits vary across demographic characteristics, lines indicating the most common limit will be displayed. The shift table will include the number and percentage of patients within each baseline category (minimum value is low, normal, high, or missing) versus each treatment category (minimum value is low, normal, or high) by treatment. Patients with at least 1 result in the treatment period will be included in the

shift table. The shift from normal/high to low table will include the number and percentage of patients by treatment whose minimum baseline result is normal or high and whose minimum treatment result is low. Patients whose minimum baseline result is normal or high and have at least 1 result during the treatment period are included. The Fisher's exact test will be used to compare percentages of patients who shift from normal/high to low between treatments.

The 3-panel display to assess high values will be created similarly. The scatterplot will plot the maximum value during the baseline period versus the maximum value during the treatment period. The shift table will include the number and percentage of patients within each baseline category (maximum value is low, normal, high, or missing) versus each treatment category (maximum value is low, normal, or high) by treatment. The shift from normal/low to high table will include the number and percentage of patients by treatment whose maximum baseline result is normal or low and whose maximum treatment result is high. Patients whose maximum baseline result is normal or low and have at least 1 result during the treatment period are included. The Fisher's exact test will be used to compare percentages of patients who shift from normal/low to high between treatments.

The low/high displays will be created for the Maintenance Period as well, but no statistical comparisons are planned and only summaries will be produced.

For laboratory analyte measurements collected qualitatively, a listing of abnormal findings will be created. The listing will include patient ID, treatment group, laboratory collection date, analyte name, and analyte finding.

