The percentages of patients with treatment-emergent high or low vital signs and physical characteristics results at any time will be summarized. A treatment-emergent high result is defined as a change from a value less than or equal to the high limit at all baseline visits to a value greater than the high limit at any time that meets the specified change criteria during the treatment period. A treatment-emergent low result is defined as a change from a value greater than or equal to the low limit at all baseline visits to a value less than the low limit at any time that meets the specified change criteria during the treatment period. To assess increases, change from the maximum value during the baseline period to the maximum value during the treatment period will be used. To assess decreases, change from the minimum value during the baseline period to the minimum value during the treatment period will be used. [Table 6.4](#) will be used to define the low and high limits and change thresholds. The low/high displays will be created for the Maintenance Period as well, but no statistical comparisons are planned and only summaries will be produced.

Additionally, values at each visit (starting at randomization) and change from baseline to each visit for vital signs and physical characteristics will be displayed in box plots (with outliers displayed) for patients who have both a baseline and a result for the specified visit. Baseline will

be the last non-missing observation in the baseline period. Original-scale data will be used for the display. Unplanned measurements will be excluded. Reference limits will not be displayed. The following summary statistics will be included in a table below the box plot: N, mean, standard deviation, minimum, Q1, median, Q3, and maximum. P-values and confidence limits will not be included in the summary statistics at the bottom of the box plot. Box plots will be used to evaluate trends over time and to assess a potential impact of outliers on central tendency summaries.

Table 6.4. Categorical Criteria for Abnormal Treatment-Emergent Blood Pressure and Pulse Measurement, and Categorical Criteria for Weight and Temperature Changes for Adults

Parameter	Low mmHg	High mmHg
Systolic BP (mm Hg) (Supine or sitting – forearm at heart level)	≤ 90 and decrease from baseline ≥ 20	≥ 140 and increase from baseline ≥ 20

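### The SAP omits the protocol's Week 16 Maintenance safety baseline for the 300 mg Q8W group, so a laboratory or vital-sign abnormality that began on placebo can be counted as treatment-emergent on 300 mg Q8W

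*SAP*

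**What the plan says.** Protocol 10.3.1.2 sets two baselines for Maintenance safety. For placebo subjects and PASI 90 non-responders, "baseline is defined as the last available value before the treatment reassignment in the maintenance period (Week 16, Visit 7". For subjects "who did achieve PASI 90, baseline is defined as the last available value before the initial randomization", which is usually Week 0.

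SAP 6.1.2.2 sets one baseline for efficacy, health outcomes and safety: "study baseline is defined as the last non-missing assessment (including unscheduled visits) before the first injection". It has no version for Maintenance, and the Week 16 rule appears nowhere else in the SAP.

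The SAP does plan Maintenance displays that depend on a baseline. SAP 6.12 lists a reduced set of safety outputs that closes with "TE high/low labs, TE high/low vitals) will be needed for the Maintenance Period". SAP 6.12.4 says of the laboratory displays: "The low/high displays will be created for the Maintenance Period as well". SAP 6.12.5 says the same for vital signs. The Maintenance columns are three PRN arms and one pooled arm, "LY 300 mg Q8W (including subjects from 4 Induction Period treatment groups" (SAP Table 6.1).

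**The concern.** The low/high displays depend directly on which values count as baseline. The laboratory table for shifts to high is restricted: "Patients whose maximum baseline result is normal or low and have at least 1 result during the treatment period are included". The table for shifts to low mirrors it. A treatment-emergent high vital sign is a "change from a value less than or equal to the high limit at all baseline visits" to a value above the limit that also meets a change criterion. Neither section says which visits are the baseline period or baseline visits once the display moves to Maintenance.

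This matters most for the 300 mg Q8W column. It is the only continuous-dosing column, at the top dose, and it mixes subjects who spent Induction on placebo with subjects who spent it on LY3074828. If Week 0 is used, a shift that happened on placebo can be reported as having emerged on 300 mg Q8W. Safety and tolerability is a secondary objective, and the two documents can yield different Maintenance tables from the same data.

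**Working it through.** **1. The two rules applied to one subject.** Take a placebo subject whose analyte is normal at Week 0, high at Week 16 before the first 300 mg dose, and still high at a Maintenance visit.

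| | Protocol baseline (Week 16) | SAP baseline (before first injection) |
|---|---|---|
| Baseline category | High | Normal |
| In denominator of normal/low-to-high table | No | Yes |
| Counted as shift on 300 mg Q8W | No | Yes |

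Both numerator and denominator change. The vital-sign rule gives the same contrast, provided the change criterion is met against Week 0.

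**2. Week 16 values.** SAP 6.1.2.1 starts Maintenance on the date of the Week 16 PASI. The protocol's Schedule of Activities has visit procedures done before dosing. SAP 6.12 allocates safety events on that date to Maintenance and does not say whether this covers laboratory and vital-sign values. If it does, a pre-dose Week 16 abnormality could count in Maintenance even if it resolves by the next visit.

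**3. Opportunity.** Hematology, chemistry and vital signs are scheduled at Visits 3 to 7. That is 5 visits after the first dose up to Week 16, and none is baseline under SAP 6.1.2.2.

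**4. Size of the group.** The inputs come from SAP 5.2: 50 per arm, with PASI 90 rates of 60% on LY3074828 and 3% on placebo. As a check on these inputs, an exact enumeration of the two-sided Fisher test at 0.05 gives power above 99.99%, consistent with the SAP's figure of over 99%. The present point does not rest on that power.

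With full arms and no dropout, and r the LY3074828 response rate:

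Group size = 50 + 3 × 50 × (1 − r)

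- r = 60%: 50 + 60 = 110; placebo share 50/110 = 45%
- r = 40%: 50 + 90 = 140; placebo share 50/140 = 36%
- r = 80%: 50 + 30 = 80; placebo share 50/80 = 62.5%

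SAP 5.2 also gives simulated counts of 9, 18 and 22 PRN subjects at Week 20, which suggest that response rises with dose. If these are scaled so that the 300 mg arm has 30 responders (this assumes equal accrual across arms), responders are 12.3 + 24.5 + 30.0 = 66.8. Non-responders are then 150 − 66.8 = 83.2, the group is 133.2, and the placebo share is 50/133.2 = 37.5%. This lies inside the range above.

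**5. Illustrative counts.** Let q be the share normal at Week 0, abnormal at Week 16 and still abnormal in Maintenance, for one abnormality. The documents give no value, so q is an assumption.

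| q | Ex-placebo subjects (50 × q) | LY3074828 non-responders (60 × q) |
|---|---|---|
| 2% | 1.0 | 1.2 |
| 5% | 2.5 | 3.0 |
| 10% | 5.0 | 6.0 |

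The first column is onset on placebo shown under 300 mg Q8W. The second is only a difference in classification between the two documents.

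**The case against.** Several counterarguments have force.

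- **The baseline is undefined, not fixed at Week 0.** SAP 6.1.2.2 defines a single study-baseline value. The displays use a minimum or maximum over a baseline period, or all baseline visits, and SAP 6.12 sends only change-from-baseline analyses to Section 6.1.2. A programmer could choose Week 16. This stands. A reader might infer that the SAP prescribes Week 0 here and that the tables will be wrong; the text supports only that they can be.
- **The protocol has no treatment-emergent rule for laboratory values or vital signs.** Protocol 10.3.4 plans mean changes and incidence of abnormal values. The contrast above joins the protocol's baseline to the SAP's shift rule. That is true, but it is the natural joint reading, because the protocol states its baseline for Maintenance safety and leaves complete analysis details to the SAP.
- **The laboratory shift tables are not all restricted.** The full shift table in SAP 6.12.4 admits anyone with a result in the treatment period and shows every baseline category, including missing. Only the normal/high-to-low and normal/low-to-high tables are restricted. A reader might infer that the whole laboratory display changes its admission rule; it does not.
- **Not every carried-over shift is misattributed.** For LY3074828 non-responders the shift arose on drug, and a Week 0 baseline keeps it visible where a Week 16 baseline hides it. This stands, and only the ex-placebo part is clear misattribution.
- **A single Week 16 value is imperfect.** A placebo subject abnormal at Week 12, normal at Week 16 and abnormal at Week 20 still counts on 300 mg Q8W. The PRN columns would also follow a different rule. Both are true, and both follow from the protocol's own definition.
- **Timing.** SAP version 2 (June 2017) predates amendments (a) and (b). The summary for (b) lists no change to 10.3.1.2, and the documents do not show whether (a) changed it. No order of drafting can be inferred, but the texts as they stand disagree.

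The by-patient vital-sign listing and the hepatic patient profiles allow some cross-checking but do not correct the summary tables.

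**Conclusion.** The point holds as a mismatch between protocol and SAP that leaves the Maintenance low/high displays open to misattribution. It affects the treatment-emergent high/low vital-sign summaries and the two restricted laboratory shift tables, in the 300 mg Q8W column. The PRN columns are essentially untouched, since both documents use about Week 0 for them.

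About 45% of the Q8W column would be ex-placebo at the SAP's 60% scenario (36% to 62.5% for response rates of 40% to 80%), assuming full arms and no dropout. The 1 to 5 ex-placebo subjects per abnormality rest wholly on an assumed shift rate of 2% to 10%. No percentage-point inflation is claimed, because the denominator itself depends on the baseline.

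A reader might take this as a threat to the trial's inference. The documents do not support that: Maintenance safety is summarized without comparisons, and neither a test nor the primary endpoint is affected. It should be fixed because the protocol already states the rule and the remedy is cheap.

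**What to change.** In SAP 6.1.2.2, 6.12.4 and 6.12.5, for the Maintenance low/high laboratory and vital-sign displays:

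1. For all placebo subjects and all PASI 90 non-responders, use the last value before the Week 16 reassignment as baseline, as protocol 10.3.1.2 does.
2. For PASI 90 achievers in the PRN arms, keep the pre-first-injection baseline.
3. State that Week 16 pre-dose values are baseline, and not Maintenance values, for the Q8W group.
4. Footnote that the baseline differs between the Q8W and PRN columns.
5. Keep a supplementary Week 0-baseline display for LY3074828 non-responders, so that persisting shifts that began on drug stay visible.

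If a single baseline is intended, state and justify the departure from protocol 10.3.1.2 in the SAP and in the clinical study report; protocol 10.3.1 requires the latter for changes to analysis methods.

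The cost is SAP wording, derivation flags and a little extra programming, with no new data. The downside is one table whose columns have different baselines.
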